Exclusion Criteria:

- Younger than 18 years of age
- History of heparin-induced thrombocytopenia (HIT)
- Patients without initial or post-administration INR readings
- Patients with an initial INR <2
- Pregnant patients
- Prisoners

2.4 If you are not using the entire population of interest, what is the method for obtaining a subset or sample of this population?

X	Not Applicable
---	----------------

2.5 Will you need to perform “preparation for research” activities prior to consenting subjects for research?

	No
	Yes
X	Not Applicable

If you answered yes above, appropriate preparation for research activities prior to consenting subjects must include the following process to determine inclusion/exclusion criteria:

- 1) Study staff will work with the PI to determine the methods used in identifying potential subjects for the research. For example, this may include creating an Epic Workbench report of patients who are in the hospital and meet minimum criteria for the research.
- 2) Study staff may access medical records of all potential subjects' identified (i.e., Workbench) to determine eligibility criteria using information that already exists in the medical record. During this process, no identifiable information may be recorded and any documentation made of a potential subject's information that would disqualify them will be destroyed.

If an eligible patient is not being cared for by the PI, study staff must approach the patient's provider to determine if it is appropriate to proceed with the consent process.

- 3) If additional testing needs to be done to see whether a patient meets criteria for entry into the study, the PI or staff will need to consent the patient first.
- 4) If the preparation activity confirms a patient is a possible subject, PI/staff approaches the patient to begin the consent process.

2.6 Describe the steps in your recruitment process.

Not Applicable

Screening and Enrollment

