patient does receive the additional 500 IU dose, the patient will be included in the intent-to-treat (ITT) analysis and considered a treatment failure for fixed dosing. (NOTE: this should be based on INR – not subjective assessment of bleeding)

All patients on chronic anticoagulation with warfarin who present with an emergent bleed or need for urgent surgery will obtain an initial INR value via the iSTAT point of care test and a laboratory INR. Due to urgent need for administration of 4FPCC, the laboratory INR may not be evaluated prior to randomization. After patient enrollment and randomization, the patient will receive the study medication and have a laboratory INR drawn 15 minutes post-administration. Obtaining a pre- and post-INR laboratory value is standard of care in the emergency department. The laboratory INRs will be utilized in all cases to evaluate the change in INR from pre- to post-administration of 4FPCC. The INRs will be collected and documented in the EMR by the treating RN. All patients enrolled in the study will be evaluated and identified via the EMR for development of a thromboembolic event within 7 days post 4FPCC administration. A 7-day follow-up period was chosen based on other studies evaluating a 4FPCC fixed dose [11,12]. Enrolled patients will be prospectively followed throughout admission with daily chart review to determine if a thromboembolic event occurred. The last patient progress note written within the 7-day follow-up period will be evaluated. This will allow us to include all patients who might have been discharged prior to the 7-day period, but were readmitted with a thromboembolic event.

2.8 Provide a brief, sequential, bullet-point description of the all the data collection activities you will conduct from start to finish (e.g., chart review, patient survey, follow-up visits, data pull from the electronic medical record, etc.) and who will conduct each. Please see our [Example of Data Collection Steps](#).

The current study will assess patient data among enrollees for the outcomes presented in section 1.1:

- 1) Treating physician will notify CCRC intern of potential study patient or the intern will notice the patient on the ED Track Board and notify the physician
- 2) Patient identification and inclusion/exclusion screening performed by the ED research intern or CCRC researcher
- 3) Physician approves the enrollment into the study

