****3. ANALYSIS****

3.1 Describe the statistical methods that will be used to address the study aims. For each aim, this will usually include:

- Description of the sample used for the particular analysis
- The variables included in the specific analysis and their role in the analysis
- Numeric summaries computed (e.g., mean, standard deviation, proportion, correlation)
- A summary of data exploration and presentation activities (e.g., generating scatter plots, summary tables)
- Description of statistical tests (e.g., independent samples t-test, Mann-Whitney test), and models constructed (e.g., logistic regression)

Please see our [Examples of Statistical Methods](#).

Describe here:

Note: Please reference the area/pages of an established protocol if you are not writing your own analysis plan.

The analytic study population will consist of patients enrolled during the study period who meet the inclusion/exclusion criteria in Section 2.3 – namely, adults on long-term warfarin therapy who present to the ED with emergent bleeding, or who are in need of urgent invasive surgical procedures. The exposure of interest will be fixed vs. variable dose 4FPCC, to which eligible patients will be randomly assigned in a 1:1 ratio. To evaluate the success of randomization, we will summarize patient demographics and relevant clinical factors by 4FPCC dosing assignment group, and conduct appropriate statistical tests (Fisher's exact test for categorical variables; Wilcoxon test for continuous variables) to identify any differences in the distributions of these factors. If there are no significant differences ($p < 0.05$) found, we will assume successful randomization, and subsequent statistical analyses will not additionally account for covariates.

(Primary) Aim 1: Fixed vs. variable dose 4FPCC and anticoagulation reversal

To evaluate whether fixed dose 4FPCC is acceptably comparable to variable dosing with respect to anticoagulation reversal, as defined by a targeted INR of ≤ 1.5 , we will employ an active-controlled non-inferiority approach to analysis of a randomized trial [D'Agostino 2003]. In order to establish non-inferiority of fixed dosing, we will test the following null and alternative hypotheses:

- $H_0: F - V \leq M$ (Variable dosing is superior to fixed)
- $H_1: F - V > M$ (Fixed dosing is not inferior to variable)

where V = variable dosing, F = fixed dosing, and M = the non-inferiority margin.

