Based on previous literature [D'Agostino 2003, Goldstein 2015] and the available study sample, we propose to set the non-inferiority margin M to -0.1. In other words, if the proportion of warfarin reversal among fixed dose patients is no worse than 10% less than the proportion of warfarin reversal among variable dosed patients, then we will reject the null hypothesis (superiority of variable dosing), and consider the fixed dose to be acceptably non-inferior to variable dosing.

Results to be reported for this aim will consist of the proportion of reversal for each group, the risk difference (RD; the proportion of reversal in fixed group minus the proportion of reversal in variable group), and the risk ratio (RR; the proportion of reversal in fixed group divided by the proportion of reversal in variable group), along with 95% confidence intervals and p-values as appropriate. Non-inferiority will be established if the lower bound of the RD is greater than the pre-specified margin M (-0.1). The primary analysis will use an intent to treat (ITT) approach (fixed vs. variable treatment assignment); however, we will also conduct supplemental analyses using an 'as treated' or 'per protocol' (PP) approach, in which we will compare patients' actual received dose (regardless of assignment) with respect to successful reversal of anticoagulation. We expect the PP approach to complement the primary ITT results, and will be informative particularly if there is non-trivial overlap in dosing by assignment group.

(Secondary) Aim 2: Fixed vs. variable dose 4FPCC and thromboembolic events

Study patients will be followed for 7 days post-administration of 4FPCC for thromboembolic events, as defined in Section 2.12. For this outcome, we will calculate and report the risk (proportion of patients experiencing an event in each group), RD, and RR, with 95% confidence intervals and p-values, as described in Aim 1. While we expect the risk of thromboembolic events to be lower in the fixed dose group, due to the limited number of anticipated thromboembolic events in the study population, the study will not specifically be powered to detect statistically significant differences by dosing group.

(Secondary) Aim 3: Fixed vs. variable dose 4FPCC and costs

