Cost outcomes will be assessed for all study patients and compared by dosing assignment. Generalized linear regression models will be constructed to estimate the difference in cost attributable to dosing assignment (β estimate), along with 95% confidence intervals and p-values. Specifications of the statistical models constructed will be dictated by the empirical distribution of cost outcomes, which we anticipate will be non-normal. In this case, the negative binomial distribution or other modeling assumptions may be used as appropriate.

Sample size:

3.2 What is the estimated sample size(s) for the primary study analyses (per group for studies with different arms or comparison groups)?

Preliminary data from Regions Hospital identified 67 patients treated with 4FPCC from January 2015 through May 2016, suggesting that we can expect about 4 eligible patients per month. Thus for a 1-year study we anticipate 48 patients in our study population, with approximately 24 patients in each dosing group. We will request approval to enroll up to 60 patients as more may present to the Emergency Department compared to our historical data.

3.3 The sample size selected was (check all that apply):

	Based on data likely to be available during a specific time period (often based on data available in past periods)
	To conduct one or more specific analyses with adequate statistical power
	To achieve a specified level of precision in one or more key estimates
	Other (explain):

3.4 Explain your choice of the sample size selection you listed above:

Sample size for this study will directly depend on the number of eligible patients on warfarin who present to the ED with bleeding emergencies during the study period.

3.5 Describe your assumptions concerning data available for analysis (e.g. How many subjects will be randomized, possibly lost to follow-up or a procedure? What do you expect for survey response rates, and how much missing data do you expect?). Include information as it pertains to your study (human or animal).

Our primary assumptions regarding available data include: 1) successful enrollment of eligible patients into the study; 2) complete data collection for relevant study variables; and 3) an even distribution of random assignment (1:1).

Missing data should be minimal, as the relevant clinical measures under evaluation are routinely documented in this context.

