We also expect loss to follow-up to be minimal, as the observation period for a given patient is very short (INR can be evaluated within 15 minutes of 4FPCC administration), and it will be unlikely for patients to leave the hospital prior to collection of relevant measures during an emergency care situation. Though it is possible patients may die during hospitalization, sufficient information should be available for these individuals to contribute to the analysis, with the possible exception of Aim 2 (thromboembolic events).

Power analysis

NOTE: If you are doing a descriptive study (i.e., aside from computing confidence intervals you are not using statistical tests, inferential statistical testing for group comparisons, or statistical models), please complete 3.6 and skip 3.7-3.8.

If you are conducting statistical tests, using statistical inference to compare groups, or are building statistical models, please skip 3.6 and complete 3.7-3.8. **Please see our Example Power Analysis.**

3.6 Provide a measure of the precision of your estimates for key study endpoints, (e.g., 95% confidence intervals on proportions or means), using actual expected estimates.

N/A

3.7 What level of differences observed in your primary endpoints would be considered clinically or practically significant?

As dictated by the active-controlled non-inferiority approach, we will consider the fixed dose of 4FPCC to be non-inferior to variable dosing if the proportion of anticoagulation reversal is no worse than the specified difference margin of -10%.

3.8 What is the power for your primary analysis (and the set of assumptions underlying it: hypothesis addressed, expected pattern of effects with justification for these expectations, analysis used, variables in the analysis, effect sizes, sample sizes, alpha level, one or two-sided test)?

Assuming available treatment group samples of N=24, a non-inferiority margin of -0.1, an alpha significance level of 0.05, an expected targeted reversal proportion in the variable dosing group of 0.77 (pooled estimate from 13 previous studies) [Khorsand 2015], and a true difference in proportions of 0, we will have 22% power to detect non-inferiority of fixed vs. variable dosing of 4FPCC.

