3.9 What are the limitations of the proposed approach and analysis?

The primary limitation will be low statistical power to reject the null hypothesis (superiority of variable dose 4FPCC), given limited sample size. Additionally, due to the nature of the intervention, blinding of treatment dosage assignment will not be feasible. Finally, patient follow-up for thromboembolic events at 7-days post 4FPCC administration may not be achieved in all patients due to discharge.

3.10 Please name the people who completed the analysis section of this application.

[name], MPH

3.11 Please name the people who will summarize data and conduct statistical analysis.

[name], MPH, and/or another member of the HealthPartners Institute Research Methodology Group.

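### Section 2.3 excludes patients with no post-dose INR and Section 3.1 builds the analysis set on that rule, so an analysis called ITT drops randomised patients on a post-randomisation event

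*Combined protocol and SAP*

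**What the plan says.** - Section 2.3, exclusion criteria: "Patients without initial or post-administration INR readings".
- Section 2.7, timing of that reading: "After patient enrollment and randomization, the patient will receive the study medication and have a laboratory INR drawn 15 minutes post-administration".
- Section 3.1, analysis set: "The analytic study population will consist of patients enrolled during the study period who meet the inclusion/exclusion criteria in Section 2.3".
- Section 3.1, Aim 1: "The primary analysis will use an intent to treat (ITT) approach", by assigned arm. Non-inferiority is declared if the lower limit for the risk difference (fixed minus variable) lies above -0.1.
- Section 3.5: "Missing data should be minimal". Of patients who die in hospital it says that "sufficient information should be available for these individuals to contribute to the analysis", with a possible exception only for thromboembolic events.
- Section 3.9: "blinding of treatment dosage assignment will not be feasible".

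The only post-randomisation event with an explicit ITT rule is the additional 500 IU in the fixed arm (Section 2.7). Those patients stay in and count as failures. There is no rule for a patient without a post-dose INR.

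**The concern.** Eligibility has to be settled before the envelope is opened, and a post-dose reading does not exist then. The criterion can therefore act only after randomisation, and Section 3.1 carries it into the primary analysis set. That departs from ITT in the ordinary sense. It also fits badly with Section 3.5, because a patient who dies before any post-dose sample would be excluded rather than contribute.

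Patients who never get a post-dose INR may differ from those who do, for example because they deteriorated, and in an open-label trial the chance of being measured could differ by arm. Losing fixed-arm failures favours non-inferiority; losing variable-arm failures works against it. If the ITT label and the 2.3 rule are not reconciled in advance, the denominator may be chosen once results are known. A late INR is not affected, because Section 2.3 sets no time limit.

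**Working it through.** **Inputs.** 24 per arm, margin -0.1, alpha 0.05 (sidedness not stated), reversal 0.77 with variable dosing, true difference 0 (Section 3.8). The number missing is not given, so every missing-data scenario below is assumed.

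**The plan's own figure.** Section 3.8 states 22% power. Exact binomial enumeration with the unpooled (Wald) limit at one-sided 0.05 gives 0.220, so it reproduces. It assumes all 24 per arm are analysed. At one-sided 0.025, which matches the lower limit of a two-sided 95% interval, the same calculation gives 0.144. Both levels are shown where it matters.

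**1. Shift per missing patient.** With 0.77 reversal among measured patients, counting one missing fixed-arm patient as a failure instead of dropping them moves the risk difference by 0.77/24 = 3.2 points. Two move it 6.4 and three 9.6, against a 10-point margin.

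**2. Single-trial examples.** Lower limit = pF - pV - z × sqrt[pF(1-pF)/nF + pV(1-pV)/nV], with z = 1.960 (95%) or 1.645 (90%). Dropped patients are fixed-arm failures.

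| Fixed | Variable | Difference | 95% lower | 90% lower |
|---|---|---|---|---|
| 21/24 | 19/24 | 0.083 | -0.126 | -0.093 |
| 21/23 (1 dropped) | 19/24 | 0.121 | -0.078 | -0.046 |
| 20/24 | 19/24 | 0.042 | -0.179 | -0.143 |
| 20/22 (2 dropped) | 19/24 | 0.117 | -0.085 | -0.052 |
| 18/24 | 18/24 | 0.000 | -0.245 | -0.206 |
| 18/22 (2 dropped) | 18/24 | 0.068 | -0.168 | -0.130 |
| 18/21 (3 dropped) | 18/24 | 0.107 | -0.122 | -0.085 |
| 18/20 (4 dropped) | 18/24 | 0.150 | -0.068 | -0.033 |

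The first pair changes the decision at 95% but not at 90%, where 21/24 already passes. The second changes it at both. With 18/24 in each arm it takes four exclusions at 95%, or three at 90%.

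**3. False non-inferiority at a true difference of -0.10 (0.67 versus 0.77).** Exact enumeration with the Wald limit, for 0, 1, 2 and 3 patients removed:

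| Patients removed | One-sided 0.05 | One-sided 0.025 |
|---|---|---|
| Fixed-arm failures | 5.5, 9.4, 15.6, 23.7% | 3.0, 5.6, 10.3, 17.5% |
| Variable-arm failures | 5.5, 3.2, 2.1, 1.4% | 3.0, 1.7, 1.1, 0.6% |
| Fixed-arm, unrelated to outcome | 5.5, 5.6, 5.8, 5.5% | 3.0, 3.1, 3.3, 3.2% |

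The normal approximation gives the same pattern for fixed-arm failures. With m dropped, pF' = 0.67 × 24/(24-m) = 0.699, 0.731, 0.766 and SE = 0.1285, 0.1277, 0.1262 (0.1288 at m = 0). The rate is Phi((pF' - 0.77 + 0.10)/SE - z): 5.0% rising to 7.8, 12.1 and 18.8% at z = 1.645, and 2.5% rising to 4.2, 6.9 and 11.5% at z = 1.960.

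**4. How often a decision would change.** With 0.77 in both arms, removing one fixed-arm failure changes the decision in about 8 to 10% of trials, and removing two in about 22 to 24% (one-sided 0.025 and 0.05 respectively).

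**The case against.** The strongest reply is that the two parts of Section 3.1 can be read together: the first says who is in the set, and the ITT label only says that patients are compared by assigned arm. On that reading there is one primary set, a modified ITT, under a loose label. This is a possible reading, but it confirms that randomised patients are dropped on a post-randomisation event. The short description of the population that follows in 3.1 does not repeat the INR criterion, but it exempts no criterion either.

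The second reply is that missing values should be rare. A post-dose INR is standard of care (Section 2.7), and Section 3.5 expects little missing data and few early departures. Its remark on deaths is an expectation, not a rule, and conflicts with 2.3 only if death precedes any post-dose sample. This bears on how likely the problem is; it supplies no rule for when it occurs.

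The third reply is that the inflated error rates assume every excluded patient is a failure and all are in one arm. That is so, and nothing in the plan predicts such a pattern. The third row of the error table shows almost no inflation when loss is unrelated to outcome. The decision examples are also chosen near the margin. These points limit the expected harm but do not make the rule sound.

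**Conclusion.** The concern holds. Followed as written, Sections 2.3 and 3.1 exclude randomised patients because of something that happens after dosing, under an ITT label, with no rule that restores or scores them. With about 24 per arm, one or two outcome-related exclusions in one arm can reverse the conclusion, although not in every table. Bias can go in either direction. It is negligible if loss is unrelated to outcome, and zero if every patient has a post-dose INR. The sizes rest on assumed missing counts and on the 0.77 planning rate; the textual defect rests on no assumption. It should be corrected before analysis because it determines the primary denominator.

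**What to change.** 1. In Section 2.3, delete the words 'or post-administration' from the INR criterion.
2. In Section 3.1, define the primary analysis set as all randomised patients in their assigned arm.
3. State in advance how a missing post-dose INR enters the primary endpoint, for example as not reversed, and report the number missing by arm.
4. Add a best/worst-case table by arm. No single rule is safe alone in a non-inferiority trial: with 2 of 24 missing per arm and counted as failures, a true deficit of -0.10 shrinks to -0.10 × 22/24 = -0.092.

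The cost is a few sentences and one small table. Reported reversal proportions may be slightly lower. No extra patients, visits or measurements are needed.

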The ED research interns and CCRC research staff will be utilized to identify eligible patients. When a patient presents with an emergent bleed or requiring emergent surgery and is on chronic warfarin anticoagulation requiring 4FPCC use, the physician will notify the ED research intern or CCRC staff. The ED research intern or CCRC researcher will determine eligibility and review inclusion and exclusion criteria with the treating physician. In addition, the CCRC intern is always in the emergency department and may notice a potentially eligible patient on the ED Track Board in EPIC. The intern would then notify the physician if he or she were not already aware of the patient. If a patient is determined to be eligible and the physician approves enrollment into the study, the CCRC intern will immediately proceed with randomization. Once the patient is randomized, the physician will be notified of the dosing order from the randomization and the physician will place the appropriate order. Due to the emergent nature of this condition, randomization envelopes will be in a locked area in the Emergency Department in order to expedite randomization and not impede urgent treatment.

Following randomization, the patient will either receive either a fixed or variable dose of 4FPCC per study protocol.

CCRC interns will abstract the study data points from the patient's EMR while the patient is in the Emergency Department

and again at the time of discharge. The variables listed on the attached data collection form will be incorporated into a secure RedCap database that the interns will use to enter the data. All patients will be identified in RedCap with a study ID number that is not linked to identifying information in the database.

Randomization

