Given the emergent nature of need for care with this clinical population, randomization will need to happen quickly following the physician decision to use 4FPCC for bleeding reversal. The CCRC intern is in the emergency department 24/7 and is able to respond quickly to the needs of patients upon physician request. This study will utilize a permuted block randomization schedule to allow for equal allocation of subjects in each arm. Given that we expect to enroll 4 patients per month over a 1-year time period, allowing for a total sample size of 48 patients (24 per group), the randomization scheme will consist of 12 permuted blocks of four. Sealed envelopes with the dosing arm (fixed vs. weight-based) will be in the research file in the locked medication room located in Pod E. Pod E is the area of the emergency department reserved for the most acute patients and is where these patients will be treated. All interns have badge access to the medication room. A filing box containing documents specific to ED research is located in the medication room. Once the treating physician deems a patient eligible, the intern will retrieve the envelope from the medication room; open the envelope and the physician will enter the order. We do not anticipate that randomization will take more than 20-30 seconds and thus will not delay patient care or treatment.

Staff Training

CCRC Intern Group

[name] will train the CCRC intern group at the monthly intern dinner in January 2016. Training will involve a PowerPoint presentation reviewing the background and significance of this study as well as the aims and hypotheses. The interns will be trained on the full study protocol with emphasis on the inclusion and exclusion criteria. [name] will also review a mock patient for data abstraction to ensure that everyone is getting data points in the EMR from the same location. [name] will train interns on the randomization procedure.

ED Staff Training

- All attending physicians will be informed of the study at the monthly ED faculty meeting in January. [name] will lead this presentation and will answer any questions.
- Residents will be informed of the study during the monthly Resident Rounds in January. This is a monthly 4-hour meeting that is mandatory for all ED residents. [name] attends this meeting and will present the study to the residents.

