- ED nursing staff will be informed about the study during daily huddles in the Emergency Department. Huddles are held three times daily for the nursing staff so that all shifts are informed. CCRC staff will attend the huddles to inform nursing staff of the study and answer any questions. We have utilized this method of education in the past and it is the best way in which to reach all nursing staff. We will attend huddles for the two weeks prior to study start.

ED Pharmacy Staff

ED pharmacy staff will be fully trained on the protocol by [name] and [name]. [name] is a senior pharmacist in the emergency department and is the primary investigator on this study. [name] is a PGY-1 Pharmacy Resident at Regions Hospital and is a Co-Investigator on this study. Both [name] and [name] will participate in training the pharmacy group.

2.7 Describe any interventions that are used in this study.

	Not Applicable
--	----------------

Eligible patients will be randomized in a 1:1 fashion to receive either a fixed dose of 1500 IU or the FDA-approved variable dosing based on body weight and presenting INR. The FDA-approved variable dosing algorithm is as follows: initial INR 2-3.9: 25 IU/kg (maximum dose 2500 IU), initial INR 4-6: 35 IU/kg (maximum dose 3500 IU), and initial INR >6: 50 IU/kg (maximum dose 5000 IU). The patient weight will be obtained using a scale and documented by the treating RN.

Randomization will be initiated with the research team member notifying the attending physician of patient enrollment, and the physician placing the order that is immediately visible in EPIC to the IV pharmacist preparing the medication. The pharmacist will prepare the study medication as either the fixed or variable dose. Exact doses of 4FPCC administered may vary slightly from the calculated doses as the amount of 4FPCC differs based on the vials utilized. The doses are unable to be blinded by the research team, as the fixed dose will have less drug volume.

Following the randomization to study doses, the patient will be monitored for continued bleeding by the treating physician. If the patient receiving the 1500 IU fixed dose remains in a bleeding state and the INR remains above goal, an additional 500 IU may be administered at the physician's discretion to minimize bleeding and attempt to achieve hemostasis. If a

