2.10 Describe your plans for ensuring data security

This study involves only minimum necessary data, in which only de-identified data will be reported. Data will be entered and stored in an HP secure RedCap database. All patients in the RedCap database will be identified only by their assigned study ID number. The database linking the patient MRN and ID number will be stored on a password-protected CCRC share drive that is only accessible to CCRC assigned staff. All electronic identifiers will be destroyed from Regions Hospital computers at the time of manuscript completion. There will not be paper data collection records for this study.

2.11. List the KEY variables that will be collected to support the study aims outlined in item 1.1. KEY variables include those used for:

- 1) achieving the study aims (outcomes, predictors, potential confounders),**
- 2) identifying the study population (for inclusion/exclusion criteria),**
- 3) describing the study population**

Please see an [Example of a Completed Table](#) and an [Example Data Dictionary](#).

Variable Name	Data Source (patient survey, EMR, claims, registry)	Purpose (sample identification, description, grouping variable, study endpoint, predictor, covariate)	Measurement Scale (binary, continuous)
Presenting INR (iSTAT and laboratory value)	EMR	Study endpoint	Continuous
Time of initial INR draw (iSTAT and laboratory value)	EMR	Variable	Continuous
INR at 15 minutes post-administration of 4FPCC	EMR	Study endpoint	Continuous
Dose of 4FPCC in IU	EMR	Study endpoint	Binary
Time to administration of 4FPCC in minutes	EMR	Study endpoint	Continuous
Administration of additional 4FPCC in fixed dose arm	EMR	Study endpoint	Binary
Thromboembolic events within 7 days	EMR	Study endpoint	Binary
Timing of thromboembolic event	EMR	Study endpoint	Continuous

Patient charge of 4FPCC in dollars	EMR	Study endpoint	Continuous
Institution cost of 4FPCC in dollars (cost per unit)	Biocare	Study endpoint	Continuous
Weight (kg) at presentation	EMR	Covariate	Continuous
Use of other reversal agents (vitamin K and FFP)	EMR	Covariate	Binary
Age	EMR	Covariate	Continuous
Indication for 4FPCC	EMR	Covariate	Binary
Attending Provider Specialty (i.e. emergency medicine, trauma, hematology/oncology, neurosurgery)	EMR	Covariate	Binary
Hospital unit (i.e. emergency department, SICU, MICU, etc.)	EMR	Covariate	Binary
Eligible patients not enrolled due to physician discretion	EMR	Covariate	Binary

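### Every block has size four in an unblinded trial, so an observer who knows the size and tracks allocations could foresee an expected third of them; the 48-slot list also stops short of the ceiling of 60.

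*Combined protocol and SAP*

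**What the plan says.** Section 2.6 (Randomization) plans 48 patients, 24 per group, and states that "the randomization scheme will consist of 12 permuted blocks of four". No section varies the block size or says that it is withheld from anyone.

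On concealment, the same section says "Sealed envelopes with the dosing arm (fixed vs. weight-based) will be in the research file", kept in a locked medication room to which all interns have badge access. Once the physician has deemed the patient eligible, an intern fetches and opens the envelope.

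On who knows what, section 2.6 (Staff Training) says "The interns will be trained on the full study protocol". Section 2.7 says "The doses are unable to be blinded by the research team", and section 3.9 lists the lack of blinding as a limitation.

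On discretion over entry, section 2.6 (Screening and Enrollment) has the intern or a researcher determine eligibility. Randomization follows "If a patient is determined to be eligible and the physician approves enrollment into the study". The variable table in section 2.11 includes "Eligible patients not enrolled due to physician discretion".

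On numbers, section 3.2 takes 67 treated patients from January 2015 through May 2016, "suggesting that we can expect about 4 eligible patients per month", and adds: "We will request approval to enroll up to 60 patients as more may present to the Emergency Department".

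**The concern.** There are two separate points.

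**Predictability.** With one fixed block size and visible past allocations, the remaining content of a block can be worked out. Once two patients in a block have gone to the same arm, the other two must go to the opposite arm; the last patient in every block is always determined. A sealed envelope hides what is inside it, but this prediction comes from earlier allocations. If the person deciding whether to put a patient forward, or whether to approve entry, can foresee the arm, that decision may depend on it. This is selection bias arising before randomization, and an intent-to-treat analysis cannot undo it. The record of eligible patients not enrolled is a partial check only: it captures physician refusals, not patients whom an intern never raises.

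**List length.** The list ends at patient 48, but approval is sought for 60. Patients 49 to 60 have no stated source of allocation. Extending the list during enrolment, by a team that has already seen 48 open allocations, is avoidable.

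**Working it through.** **Inputs.** 12 blocks of size 4, 48 patients (section 2.6); 1:1 allocation (section 2.7); ceiling of 60 (section 3.2); 67 cases in the 17 months from January 2015 through May 2016 (section 3.2).

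**The plan's own figures.** 12 × 4 = 48, or 24 per arm, as stated. 67/17 = 3.94 per month, and 3.94 × 12 = 47.3 per year, consistent with about 4 a month and 48 in a year.

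**Certain allocations, blocks of four.** A 2:2 block has 6 equally likely sequences. A slot is certain when one arm is already used up in that block. Four sequences have 1 certain slot (the last); two (FFVV and VVFF) have 2.

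- Expected per block: (4 × 1 + 2 × 2)/6 = 1.333 of 4, or 33.3%.
- Over 12 blocks: 12 × 1.333 = 16 of 48.
- Distribution: 12 + Binomial(12, 1/3), with possible range 12 to 24 and central 95% range 13 to 19.

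**Best guess, blocks of four.** The chance of a correct guess at slots 1 to 4 is 1/2, 2/3, 2/3 and 1. The mean is 2.833/4 = 70.8%, against 50% under simple randomization.

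**Alternative list.** Six blocks of 4 and six of 6 in random order give 6 × 4 + 6 × 6 = 60 slots. The alternative was simulated (3,000 lists) with an observer who updates on every allocation; the last row used 10,000 lists.

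| Observer | 12 blocks of 4: certain | 12 blocks of 4: guess right | Mixed 60-slot list: certain | Mixed 60-slot list: guess right |
|---|---|---|---|---|
| Knows the size or sizes | 33.3% | 70.8% | about 6% | 69% |
| Also knows how many blocks of each size | same | same | about 8% (4.9 of 60) | 69% |
| Knows no sizes, guesses the arm that is behind | n/a | 70.8% | n/a | 69% |

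The change removes most of the certainty and almost none of the best-guess accuracy.

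**Shortfall.** 60 − 48 = 12 slots, or three blocks of four. Assume Poisson accrual over 12 months:

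| Share of cases enrolled (assumed) | Mean | P(more than 48) |
|---|---|---|
| 100%, at 4 per month | 48 | 46% |
| 100%, at 67 per 17 months | 47.3 | 42% |
| 90% | 0.90 × 47.3 = 42.6 | 18% |
| 85% | 0.85 × 47.3 = 40.2 | 10% |
| 80% | 0.80 × 47.3 = 37.8 | 5% |

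The shares below 100% are illustrations; the documents give no enrolment fraction.

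**The case against.** The one-third figure belongs to an observer whom the documents do not show to exist: someone who knows the size, has followed every allocation and can influence entry. The roles are partly split. Interns learn the full protocol but cover the department as a group, at about four patients a month, and screen largely on firm criteria. Physicians hold the discretionary approval, and nothing says that they are told the block size. The plan also has real safeguards: sealed envelopes in a locked room, approval before opening, a record of eligible patients not enrolled, and the baseline comparison by arm in section 3.1. The remedy hardly changes best-guess accuracy and permits a larger imbalance. Finally, 60 is a requested ceiling, not a target, and three more blocks of four would reach it without any change of design.

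Much of this stands as a limit on the size of the concern. It does not remove it. The interns work as one team that screens, opens envelopes and enters study data at a single site, so the sequence is available to the group even if no one person sees all of it. Entry has soft edges: an intern may or may not notice a patient, and the indication list is open-ended. Baseline tests with about 24 per arm are a weak detector. Three more blocks of four would cure the shortfall but leave an expected 20 of 60 allocations certain. The objection on accrual also has force: 42% to 46% holds only if every eligible patient is enrolled, although section 2.6 does expect to enrol four a month.

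**Conclusion.** Both parts hold, and the plan should be changed before the first envelope is opened. For an observer who knows the block size and tracks every allocation in list order, an expected 16 of 48 allocations (33%) are certain. This measures what could be foreseen; it is not evidence that anyone would use it, and the resulting bias cannot be quantified from the documents.

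The list shortfall is a smaller and contingent gap. Under Poisson accrual the chance of needing a 49th slot is 42% to 46% if all eligible patients are enrolled, and about 5% to 18% if 80% to 90% are.

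Confidence is medium, because the importance of the first part depends on behaviour that the documents do not describe.

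**What to change.** Before enrolment starts, have the statistician generate one 60-slot list with block sizes 4 and 6 in random order, six of each. Replace the sentence in section 2.6 with, for example: *The statistician will prepare one 60-slot list in permuted blocks of varying size; block sizes are held in a restricted file.* Keep the sizes, their counts and the list out of the protocol and out of training material seen by enrolling staff. Leave the sealed, locked envelopes and approval before opening as they are.

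The cost is a new list, 60 envelopes and a one-sentence edit, with nothing added at the bedside. The downside is that the arms can differ by up to 3 rather than 2 if enrolment stops mid-block. Stopping before the end of the list is likely, since about 48 patients are expected on a 60-slot list. Predictability is reduced, not removed: guessing whichever arm is behind would still be right about 69% of the time.
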